4 STUDY DESIGN

4.1 OVERALL DESIGN

The proposed study is a single center, prospective, non-inferiority trial evaluating the efficacy of small bore (14 Fr) vs large bore thoracostomy tubes in the setting of trauma at an American College of Surgeons designated Level I trauma center. Each patient will receive a study approved thoracostomy tube as indicated and our standard of care thoracostomy tube Practice Guideline will be followed. The study period is from the time of enrollment (visit day 0) up to 90 days (± 14 days) following the date of thoracostomy tube placement. A total of 645 subjects will be prospectively enrolled.

Aim I will be achieved through a prospective randomized study design which will evaluate thoracostomy tubes placed in the setting of traumatic hemothorax or hemopneumothorax. The efficacy of the thoracostomy tube sizes will be determined by assessing the participants for retained hemothorax which will be defined in this study as any residual blood that cannot be drained after 72 hours of thoracostomy as confirmed by imaging. A total of 252 subjects will be enrolled and randomized in this study group.

Aim II will be achieved through a prospective non-randomized controlled study design in which maximum barrier precautions will be used during chest tube placement for all prospective subjects diagnosed with a traumatic pneumothorax, hemothorax or hemopneumothorax. The prospective subjects will be compared to subjects in a retrospective analysis in which the use of maximum barrier precautions was not standard. Maximal barrier precautions will consist of a thyroid drape, hand hygiene, sterile gown, mask, and gloves. The use of sterile technique will be consistent throughout the prospective study. This will limit the variability between the two treatment arms and allow a more accurate comparison of empyema rates between tube size and sterile technique. The use of prophylactic antimicrobial agents will also be collected for these subjects. A total of 645 subjects will be enrolled in this study group (inclusive of those patients enrolled as part of Aim I).

All participants will be monitored for their need for operative intervention (e.g. VATS), development of empyema, hospital readmission, tube related complications (e.g. tube misplacement, tube migration), and death which occurs between thoracostomy tube placement and follow-up.

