Number of Patients	
Aim 1: With a sample size of n=126 per group, we will have 80% power to detect a non-inferiority margin difference between the group rates of 8% (allowing up to a 15% rate of drainage failure in the small 14 tube size group and approximately 7% in the large 28 tube size group; $\alpha=0.05$).
 
Aim 2: With assumptions of empyema rate is 5% in the retrospective group and 2% in the prospective group, 586 patients in each group are needed to achieve a power of 0.8 with $\alpha=0.05$. To account for potential attrition, we will inflate the number of patients by 10% resulting in a total of 645 patients in the retrospective group and 645 patients in the prospective group.

Inclusion Criteria	
 1. The patient is admitted to the trauma service. 2. The patient has a pneumothorax, hemothorax and/or hemopneumothorax, requiring thoracostomy tube placement. 3. Thoracostomy tube placement is able to be performed or witnessed by an investigator listed on the study. 4. The patient has not had a chest tube in the past year. 5. The patient is ≥ 18 years of age. 6. In the event the patient is decisionally impaired, consent will be obtained from the individual's legally authorized representative (LAR) or from the individual's healthcare power of attorney (HPA). 7. In the instance of reversible impairment, initial consent would be obtained from the LAR/HPA and the patient will be approached for consent once he/she is deemed mentally competent by the care provider.
Exclusion Criteria	
 1. The patient is incarcerated 2. The patient is known to be pregnant 3. The patient is hemodynamically unstable, requiring emergent chest tube placement (in <10 minutes from evaluation). 4. The patient will have more than one chest tube placed at the time of enrollment.

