Outcome measures	
Aim I
 
Primary outcome:
 
 • Retained hemothorax requiring an additional intervention, either video-assisted thoracoscopic surgery (VATS) or additional thoracostomy tube placement. 
Secondary outcome:
 
 • Duration of chest tube placement [Time Frame: 90 days] • Length of hospitalization • Subjective pain [Time Frame: 5 minutes pre- and post-insertion], Assessed with 0-10 numeric pain rating scale • Hemodynamic stability post-insertion (determined by vital signs: temperature, heart rate, blood pressure, oxygen saturation) • Initial drainage from chest tube at 5 minutes [Time Frame: 5 minutes] • Tube specific complications: Air leak, tube malposition, & tube migration [Time Frame: 90 days] • Time to radiographic resolution of pneumothorax/hemothorax/hemopneumothorax [Time Frame: 90 days] • Recurrent pneumothorax/hemothorax/hemopneumothorax after tube removal • Readmission for chest tube related complications [Time Frame: 90 days] 
Aim II
 
 • Empyema rates in traumatic pneumothorax, hemothorax, and hemopneumothorax
Description of Study Intervention:	Placement of 14 Fr Thal tube or 28 Fr Chest Tube for Hemopneumothorax.
Study Duration:	2 Years
Randomization	Permuted block randomization with random block sizes to allocate patients in a 1:1 allocation to the 14 or 28 tube sizes. The randomization lists will be generated using SAS Enterprise Guide version 6.1. All study staff collecting and recording data for the trial will be masked to the tube size that was used during the procedure.

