3 OBJECTIVES AND ENDPOINTS

OBJECTIVES	ENDPOINTS
	Primary
Aim I: Determine the safety and efficacy non-inferiority between small bore (14 Fr) and large bore (28 Fr) in the drainage of traumatic hemothorax and hemopneumothorax	Endpoint I: Retained hemothorax requiring an additional intervention, either video-assisted thoracoscopic surgery (VATS) or additional thoracostomy tube placement.
	Secondary
	Endpoint II: Duration of chest tube placement
	Endpoint III: Initial drainage from chest tube at 5 minutes
	Endpoint IV: Length of hospitalization
	Endpoint V: Subjective pain score (pre- and post-insertion recorded within 5 minutes of insertion). Assessed with 0 -10 numerical pain scale
	Endpoint VI: Hemodynamic stability post-insertion (determined by vital signs: temperature, heart rate, blood pressure, oxygen saturation)
	Endpoint VII: Time to radiographic resolution of pneumothorax, hemothorax, hemopneumothorax
	Endpoint VIII: Tube specific complications: Air leak, tube malposition, & tube migration
	Endpoint IX: Recurrent pneumothorax/hemothorax/hemopneumothorax after tube removal
	Endpoint X: Readmission to hospital for a chest tube related complication

OBJECTIVES	ENDPOINTS
Aim II: Determine the incidence of empyema in the setting of traumatic pneumothorax, hemothorax, and hemopneumothorax with the addition of maximum barrier precautions	Endpoint Ia: Empyema rate

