7 STUDY INTERVENTION DISCONTINUATION AND PARTICIPANT DISCONTINUATION/WITHDRAWAL

7.1 DISCONTINUATION OF STUDY INTERVENTION

If the initial thoracostomy tube has inadequate drainage, the primary care team reserves the right to replace the tube. The patient will not be removed from the study and this data will be collected as an outcome.

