8 STUDY ASSESSMENTS AND PROCEDURES

8.1 EFFICACY ASSESSMENTS

The rates of failure of drainage (primary outcome) will be estimated as proportions and compared between the two groups using a Chi-square test corrected for the non-inferiority hypothesis. The margin of non-inferiority is defined as of 8%.

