9.2 SAMPLE SIZE DETERMINATION

Aim I

This study is a non-inferiority randomized controlled trial comparing placement of 14 French vs. 28 French chest tubes for hemothorax and hemopneumothorax. We hypothesize the rate of drainage failure to be approximately 7% in the large 28 tube size group. With a sample size of n=126 per group, we will have 80% power to detect a non-inferiority margin difference between the group rates of 8% (allowing up to a 15% rate of drainage failure in the small 14 tube size group; $\alpha=0.05$). In our prior study, we saw a 20% vs 6.7% difference in needing additional procedures for pneumothorax with small vs large catheters but these numbers are based on draining air not blood. Sample size analyses were conducted in PASS 13⁹.

Aim II

Calculations of sample size were based on two-group comparisons of empyema rates. With assumptions of empyema rate is 5% in the retrospective group and 2% in the prospective group, 586 patients in each group are needed to achieve a power of 0.8 with $\alpha=0.05$. To account for potential attrition, we will inflate the number of patients by 10% resulting in a total of 645 patients in the retrospective group and 645 patients in the prospective group. The sample size was calculated by using the PASS 15¹⁰.

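### The Aim I primary endpoint is stated in two ways that disagree, and combining them leaves out a tube replaced or added before 72 hours that then clears the blood

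*Combined protocol and SAP*

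**What the plan says.** The formal endpoint has the same wording in Section 1.1 (Outcome measures), Section 3 and Section 9.1: "Retained hemothorax requiring an additional intervention, either video-assisted thoracoscopic surgery (VATS) or additional thoracostomy tube placement". An intervention is part of it.

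Section 4.1 says that tube efficacy will be determined by assessing for retained hemothorax, which is "defined in this study as any residual blood that cannot be drained after 72 hours of thoracostomy as confirmed by imaging". No intervention is required there.

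Sections 1.1 (Statistical Analysis), 8.1, 9.4.2 and 9.4.4 analyse *failure of drainage* and tie it to the primary outcome. Section 9.2 sizes the trial on nearly the same term: "We hypothesize the rate of drainage failure to be approximately 7% in the large 28 tube size group", and the synopsis sizing text continues "allowing up to a 15% rate of drainage failure in the small 14 tube size group". Neither term is defined.

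Section 7.1 foresees early trouble with the tube: "If the initial thoracostomy tube has inadequate drainage, the primary care team reserves the right to replace the tube". It sets no time condition. It then says: "The patient will not be removed from the study and this data will be collected as an outcome". It does not say which outcome. Section 9.4.3 compares re-intervention between arms among the secondary analyses, and Section 8.2 lists the need for additional interventions, including tube replacement, as a safety endpoint.

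**The concern.** An analyst coding the primary variable has to choose between two rules, and they classify some patients differently. The natural way to reconcile them is to use Section 4.1 as the definition of the term inside the formal endpoint. That creates a gap: if the first tube drains poorly and a second tube clears the chest before 72 hours, there is no residual blood after 72 hours and so no retained hemothorax. The patient had a failed first tube and an extra procedure, yet counts as a success.

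This matters more in a non-inferiority trial than in a superiority trial, because failures left out of the count usually shrink the observed difference and favour the new device. Section 2.3.3 itself allows that 14 Fr patients may have more retained hemothorax. Few events are expected: 126 × 0.07 = 8.8 per arm. It is also unstated which event the 7% rate and the 8-point margin describe. The prior figures in Section 9.2 (20% vs 6.7%) concern additional procedures for pneumothorax, so they do not answer this.

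**Working it through.** **Step 1. Apply the wordings to three hypothetical patients.**

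| Patient | Section 4.1 alone | Sections 3 and 9.1 with 4.1 nested | Failure of drainage, in ordinary words |
|---|---|---|---|
| Residual blood on imaging after 72 h, then VATS | Failure | Failure | Failure |
| Residual blood on imaging after 72 h, no intervention | Failure | Not a failure | Unclear |
| First tube drains poorly, replaced or added to at 36 h, chest then clears | Not a failure | Not a failure | Failure |

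The second row is the disagreement between the two statements. The third row is the gap. For that patient there is a further doubt: Section 7.1 speaks of replacing a tube, Section 3 of placing an additional one.

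**Step 2. Reproduce the plan's sample size.** Inputs: equal true rates of 7% (Section 9.2), margin 8 points (Section 8.1), 80% power and α = 0.05 (Section 9.2). Sidedness is not stated.

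n = 2 × 0.07 × 0.93 × (1.645 + 0.842)² / 0.08² = 0.1302 × 6.185 / 0.0064 = 125.8, rounded up to 126 per group.

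This matches the plan with a one-sided 0.05 test. One-sided 0.025 would give 160. The arithmetic is not in dispute.

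**Step 3. Find the tipping point.** Non-inferiority is declared if d + 1.645 × SE < 0.08, where d is the 14 Fr rate minus the 28 Fr rate and SE is unpooled. Take 9/126 = 0.0714 failures on 28 Fr.

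- 11/126 = 0.0873 on 14 Fr: SE = √[(0.0873 × 0.9127 + 0.0714 × 0.9286)/126] = 0.0340. Upper limit = 0.0159 + 1.645 × 0.0340 = 0.0719. Non-inferior.
- 12/126 = 0.0952 on 14 Fr: SE = √[(0.0952 × 0.9048 + 0.0714 × 0.9286)/126] = 0.0348. Upper limit = 0.0238 + 1.645 × 0.0348 = 0.0810. Not non-inferior.

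A Farrington-Manning score test gives the same limit of 11.

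**Step 4. See how often a few reclassified patients would reverse the result.** This enumerates all pairs of binomial counts with 126 per arm and both true rates at 7%. The figures are the share of all trials that declare non-inferiority on the counted failures and would not after the addition.

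| Failures added | To 14 Fr only | To each arm |
|---|---|---|
| 1 | 8.6% | 2.4% |
| 2 | 18.9% | 4.8% |
| 3 | 30.1% | 7.2% |

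The second column is small because d does not change and only SE grows. For example, moving from 11 vs 9 to 12 vs 10 keeps d at 0.0159 and gives SE = √[(0.0952 × 0.9048 + 0.0794 × 0.9206)/126] = 0.0356, so the upper limit goes from 7.2 to 7.4 points.

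**Step 5. Power if a wider definition raises the common rate** (126 per arm, exact enumeration, assumed rates): 7% gives 80%, 8% gives 76%, 9% gives 72% and 10% gives 69%.

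**The case against.** **One endpoint, one label.** The formal wording is identical in three places, and failure of drainage is tagged as the primary outcome. A reader might infer three rival endpoints. The documents do not support that: the label points to the declared primary outcome. What remains is that the label does not say whether the intervention is required, and Section 4.1 omits it.

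**Early replacements are not lost.** They would be visible by arm under re-intervention (Section 9.4.3) and would be reviewed as a safety endpoint (Section 8.2). This is a fair point. But neither place feeds the non-inferiority test, so it limits the harm without closing the gap.

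**No time frame.** A reader might infer that the endpoint has no limit in time, since other outcomes in the same list carry one, such as "Duration of chest tube placement [Time Frame: 90 days". That goes too far. Section 4.1 sets a study period of up to 90 (±14) days, the Schedule of Activities collects additional tubes and operative interventions to Day 90, and some secondary outcomes also lack a stated window. An explicit statement is missing, but an outer bound is implied.

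**The numbers rest on assumptions.** This stands. The larger reversal figures put every extra failure in the 14 Fr arm, and any result near its margin can turn on one or two patients.

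**Conclusion.** The two statements of the primary endpoint do not agree, and nesting one in the other, the most natural reading, can undercount drainage failures. The bias favours non-inferiority if early replacement is at least as common with 14 Fr. If it were more common with 28 Fr, the bias would run the other way.

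The size is unknown, because no document gives an early-replacement rate. The illustration shows sensitivity only: one failure separates 7.2 from 8.1 points, and one to three added failures reverse 8.6% to 30.1% of trials if all fall on 14 Fr, or 2.4% to 7.2% if they fall on both arms. These figures assume 126 per arm, an unpooled one-sided 95% limit and true rates of 7%.

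Two stronger conclusions are not supported. One is that the trial's conclusion would change; nothing in the documents shows that. The other is that the type I error of the test is inflated. For the endpoint as counted, at a true 8-point difference, it stays at 5.6% to 6.1% for control rates from 7% down to 4.2%. What is at issue is which event is counted. The stated 126 per group is correct for a 7% rate.

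**What to change.** Before the 50% interim look in Section 9.4.4, reconcile Sections 1.1, 3, 4.1, 7.1, 8.1, 9.1, 9.2, 9.4.2 and 9.4.4 into one primary outcome definition:

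- Count VATS, or a replaced or additional tube, for undrained blood as a drainage failure whether it occurs before or after 72 hours, over the existing 90-day period.
- Say in Section 7.1 that a replacement for this reason counts toward the primary outcome.
- Report the imaging-only 72-hour outcome as a sensitivity analysis.
- State that the 7% rate and the 8-point margin refer to this outcome, and restate the power if the expected rate differs.

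This concerns how outcomes are classified, not when a tube should be replaced.

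**Cost.** The synopsis lists the trial as recruiting, and the Statement of Compliance requires IRB approval of any amendment. Additional tubes, operative interventions and radiologist-confirmed resolution are already in the daily log (Section 6.2), so timing against 72 hours can be derived at least to the day. The reason for a repeat tube (blood or air) is not listed there and may need chart review for patients already enrolled. The stated power may fall, to 76%, 72% or 69% at an assumed rate of 8%, 9% or 10%.

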4.3 END OF STUDY DEFINITION

The study will be complete once target enrollment has been achieved and all outcomes information is available.

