5 STUDY POPULATION

5.1 INCLUSION CRITERIA

- The patient is admitted to the trauma service.
- The patient has a hemothorax and/or or hemopneumothorax, requiring thoracostomy tube placement.
- Thoracostomy tube placement is able to be performed or witnessed by an investigator listed on the study.
- The patient has not had a chest tube in the past year.
- The patient is ≥ 18 years of age.
- In the event the patient is decisionally impaired, consent will be obtained from the individual's legally authorized representative (LAR) or from the individual's healthcare power of attorney (HPA).
- In the instance of reversible impairment, initial consent would be obtained from the LAR/HPA and the patient will be approached for consent once he/she is deemed mentally competent by the care provider.

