6 STUDY INTERVENTION

6.1 STUDY INTERVENTION(S) ADMINISTRATION

Screened subjects eligible for study participation will have their inclusion/exclusion criteria verified by an investigator. The subject will be approached for consent by the research staff and enrolled. Subjects with suspected pneumothorax alone will receive either a small bore (14 Fr) or large bore (28 Fr) tube chosen based on physician preference. Subjects with suspected hemothorax or hemopneumothorax will be randomized to receive either a small or large bore chest tube.

Enrolled subjects will have their thoracostomy tube placement procedure observed and verified by an investigator listed on this protocol. The training level of the individual performing the procedure will be recorded. Maximum barrier precautions for this study will be used during the placement procedure for all prospective subjects. Maximum barrier precautions for this study will be defined as the correct use of proper hand hygiene, a cap, surgical gown, sterile gloves, mask, and a thyroid drape. The institutional standard of care thoracostomy tube Practice Guidelines will be followed.

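### The 252 randomised, the 645 total and the uncapped randomisation rule agree only if 39.1% of enrolled patients have blood; the plan does not say which target gives way, and the crude Aim II comparison cannot separate diagnosis mix from a barrier effect

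*Combined protocol and SAP*

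**What the plan says.** Section 4.1 fixes two totals. For Aim I: "A total of 252 subjects will be enrolled and randomized in this study group". For Aim II: "A total of 645 subjects will be enrolled in this study group (inclusive of those patients enrolled as part of Aim I"), so the 252 sit inside the 645.

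Section 6.1 assigns patients by suspected diagnosis. With blood: "Subjects with suspected hemothorax or hemopneumothorax will be randomized to receive either a small or large bore chest tube". With air alone: "Subjects with suspected pneumothorax alone will receive either a small bore (14 Fr) or large bore (28 Fr) tube chosen based on physician preference". No cap is placed on either group.

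Section 4.3 gives one stopping point: "The study will be complete once target enrollment has been achieved and all outcomes information is available". It does not say whether that means 252, 645 or both.

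Section 9.2 bases Aim II on a two-group comparison of empyema rates, 5% in retrospective and 2% in prospective patients. Section 9.4 describes no analysis of that comparison and no adjustment for diagnosis. The baseline check in 9.4.1 is written for the randomised trial. Section 9.4.4 times the interim looks at 50% and 75% of information without naming the denominator.

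Eligibility is also inconsistent. Section 5.1 reads "The patient has a hemothorax and/or or hemopneumothorax, requiring thoracostomy tube placement", whereas the synopsis, 4.1, 6.1 and 9.3 also admit pneumothorax alone.

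**The concern.** Two fixed totals and an uncapped rule for who is randomised are compatible at only one case mix. At any other mix something must give way, and the protocol leaves the choice to the people running enrolment.

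Two things are at stake. Aim I, the randomised comparison, could finish below its planned size. Aim II could have its diagnosis mix set by a quota while the historical mix was set by whoever presented. If empyema risk differs between patients with blood and patients with air alone, a crude comparison then reads the difference in mix as an effect of the barrier precautions.

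**Working it through.** **Inputs from the documents.** Aim I: 126 per group, 1:1, failure rate 7% ("We hypothesize the rate of drainage failure to be approximately 7% in the large 28 tube size group"), margin 8 points (8.1), α = 0.05, 80% power. Aim II: 5% against 2%, 586 per group, plus 10%. Totals: 252 and 645. The blood share and the empyema risk by diagnosis are not given, so ranges are assumed below.

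**Reproducing the plan's figures.**
- Aim I, 7% in both arms, one-sided 0.05 (inferred from the upper confidence limit in 9.4.2): n = 2 × 0.07 × 0.93 × (1.645 + 0.842)² / 0.08² → 126 per group, power 80.1%. Total 252.
- Aim II, two-sided 0.05, unpooled variance: n = (0.05 × 0.95 + 0.02 × 0.98) × (1.960 + 0.842)² / 0.03² = 585.2 → 586. Then 586 × 1.10 = 644.6 → 645.

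**Implied case mix.** 252/645 = 39.07% with blood, leaving 645 − 252 = 393 (60.93%) with air alone. Even if the true share were exactly 39.07%, chance alone would give 228 to 276 randomised (95% range) among 645 consecutive patients.

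**Aim I, by assumed blood share p.** Randomised at 645 = 645p. Power = Φ(0.08/√(2 × 0.07 × 0.93/n) − 1.645), with n = 645p/2 per arm. Enrolment needed for 252 = 252/p.

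| p | Randomised if stopped at 645 | Power | Enrolled when 252 is reached |
|---|---|---|---|
| 25% | 161 | 64% | 1008 |
| 30% | 194 | 70% | 840 |
| 35% | 226 | 76% | 720 |
| 39.07% | 252 | 80% | 645 |
| 50% | 322 | 88% | 504 |
| 60% | 387 | 92% | 420 |

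**Interim looks.** With 252 as denominator they fall at 126 and 189 randomised. If randomisation ran on to 387, the same fractions would be about 194 and 290.

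**Aim II if both totals are held.** The prospective mix is 252:393 whatever the natural mix. Let the historical cohort have blood share s, an overall empyema rate of 5% and a risk ratio R (blood against air alone), with no barrier effect. Then:
- air-alone rate t = 0.05/(sR + 1 − s);
- expected prospective rate = t × (0.3907R + 0.6093).

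Example, s = 60%, R = 3.5: t = 0.05/2.5 = 2.0%, blood 7.0%, prospective rate 0.02 × (1.367 + 0.609) = 3.95%.

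The chance of a significant result in favour of barriers (pooled chi-square, two-sided 0.05, 645 against 645, exact binomial enumeration; nominal 2.5%) is:

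| Historical blood share | R = 1.5 | R = 2 | R = 3 | R = 3.5 |
|---|---|---|---|---|
| 45% | 3.2% | 3.7% | 4.5% | 4.8% |
| 50% | 3.8% | 4.9% | 6.7% | 7.4% |
| 60% | 5.3% | 8.0% | 12.7% | 14.6% |
| 70% | 7.0% | 12.0% | 20.4% | 23.7% |

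Below a 39% historical share the bias reverses. At 30% the chance is 1.7% to 0.7% over the same risk ratios, so a real benefit would be harder to show.

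**The case against.** A reader might infer that any share other than 39% forces one of two outcomes: Aim I stops short, or Aim II becomes artificially rich in pneumothorax. The documents do not support that. Nothing in them turns patients with blood away after 252, and nothing says enrolment closes at 645 with Aim I incomplete. There are other ways out:
- With a share above 39% and 6.1 followed as written, randomisation runs past 252. Aim I gains power (88% to 92% at shares of 50–60%) and the Aim II mix is not distorted, though 4.1 is contradicted.
- With a share below 39%, enrolment may continue past 645 until 252 are randomised. Section 4.3 can fairly be read as requiring both targets.
- With a share below 39% and pneumothorax closed at 393, Aim II becomes rich in blood, the opposite direction.

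It is also fair to say that nothing shows the true share differs from 39%, and that any single false-benefit figure rests on two unknowns, the historical share and the risk ratio. This is why a range is shown.

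What stands is that the protocol does not choose among these resolutions, and they differ in Aim I size, interim timing and Aim II bias. The crude historical comparison also leaves Aim II exposed to a difference in mix whichever one is adopted.

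**Conclusion.** The point holds as a gap in the rules and a weakness in the Aim II comparison. It does not show that either aim will fail.

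The 39.1% figure follows directly from the stated totals. The Aim I loss (power 76%, 70% or 64% at shares of 35%, 30% or 25%) applies only if enrolment stops at 645. It assumes 7% failure in both arms and a one-sided 0.05 test. The Aim II false-benefit range of about 3% to 24% applies only if both totals are held. It assumes a 5% historical rate, no barrier effect, a historical blood share of 45–70% and a risk ratio of 1.5–3.5. It falls below the nominal 2.5% if the historical share is under 39%.

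**What to change.** 1. **Aim II analysis (add to 9.4).** Compare empyema within diagnosis (blood / air alone) and standardise both cohorts to one pre-stated mix. If the precautions have no effect and risks within diagnosis are the same in both periods, the standardised difference is zero whatever each cohort's mix. Diagnosis is already among the prospective baseline data (6.2); for historical patients it would be taken from the chart.
2. **Targets (4.1, 4.3, 6.1, 9.4.4).** State that Aim I ends at 252 randomised, that 252 is the denominator for the 50% and 75% looks, and that patients with blood remain eligible for Aim II afterwards. State the expected case mix.
3. **Reconcile.** Section 6.1 has no tube-selection wording for patients with blood who are not randomised, and it must be made consistent with item 2. Section 5.1 must be reconciled with the synopsis, 4.1, 6.1 and 9.3 on pneumothorax alone; read literally with 6.1, it would have all 645 randomised.

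**Cost.** Amendment wording, a slightly more complex analysis and chart abstraction of one variable. The larger cost is enrolment. If Aim I must reach 252, about 720 patients are needed at a 35% share and 840 at 30%, a real burden for a single-centre, internally funded study planned for two years. If that is not feasible, restate the Aim I power for the number actually randomised.
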